### DLT Evaluation

A subject is not DLT-evaluable if he/she drops out before completion of the DLT window for reasons other than an adverse event related to study drug **or the subject has not received IP treatment for at least 14 days at the target dose for a 3- or 4-week cycle or at least 7 days at a target dose for a 2-week cycle**. All available safety data for subjects who are not DLT evaluable will still be evaluated and considered in DLRM decisions. No dose escalation will occur unless at least 3 subjects have **been assessed as DLT evaluable**. Duration of a cycle might be extended and be different from the duration of the DLT window. For all cohorts, the DLT window may also be extended

retrospectively to assess events starting or persisting outside the window in case the DLT definition is time dependent (eg, in case of neutropenia, see below).

Any adverse event occurring outside the DLT window that is determined by the investigator to be possibly related to the investigational product, which is seen more frequently or is more severe than expected or is persistent despite appropriate management, can be determined to be a DLT upon unanimous decision by the DLRT after review of the adverse event and all available safety data.

Events listed below are to be considered as DLTs and exceptions when occurring in a subject during the DLT window unless clearly attributable to causes other than AMG 330 treatment:

- Any treatment-related death.
- Grade 4 neutropenia lasting  $\geq$  42 days from start of cycle in absence of evidence of active AML (in case of 3 or 4 weeks treatment cycles, the number of days would increase accordingly)
- Grade 3–5 non-hematologic toxicity not clearly resulting from the underlying leukemia EXCEPT:
  - Alopecia
  - Grade 3 fatigue, asthenia, fever, anorexia, or constipation
  - Grade 3 nausea, vomiting or diarrhea not requiring tube feeding, total parenteral nutrition, or requiring or prolonging hospitalization
  - Infection, bleeding, or other expected direct complication of cytopenias due to active underlying leukemia
  - Grade 3 infusion reaction, if successfully managed and which resolves within 72 hours
  - Grade 3 rash
  - Grade 3 or 4 tumor lysis syndrome if it is successfully managed clinically and resolves within 7 days without end-organ damage.
- Grade 3 or 4 isolated electrolyte abnormalities (ie, those occurring without clinical consequence) that resolve, with or without intervention, to  $<$  Grade 2 levels in  $<$  72 hours will not be considered DLT.
- Grade 3 or 4 asymptomatic enzyme elevations including AST, ALT (without bilirubin elevation), GGT (gamma-glutamyl transferase), lipase and amylase that resolve to  $\leq$  Grade 2, with or without intervention, within 7 days will not be considered a DLT.
- CRS meeting any of the criteria listed below:
  - Grade 2 CRS that does not resolve, with or without intervention to Grade 1 within 7 days will be considered a DLT
  - Grade 3 CRS that does not resolve, with or without intervention to  $\leq$  Grade 2 within 5 days, or  $\leq$  grade 1 within 7 days, will be considered a DLT

- Grade 3 CRS reported at the initial dose (ie, at MTD1; applicable only after MTD1 has been defined) will be considered a DLT
- Grade 4 CRS occurring during AMG 330 treatment.
- Two separate grade 3 CRS events will be considered a DLT.

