### 3.1.3 Design of Group 3: MDS

The dose-escalation cohorts will estimate the MTD, safety, tolerability, PK, and PD of AMG 330 in subjects with MDS. The following dose escalation cohorts will be evaluated:

[REDACTED]

Selected

**target dose levels, with the exception of the maximal tested dose, that have been deemed safe in subjects with R/R AML (Group 1) could be skipped in Group 3 dose escalation cohorts based on available safety, PK, and PD data if recommended by the DLRT.** Administration of 8 mg IV dexamethasone within 1 hour prior to the dose step for prevention of cytokine release is mandatory. Up to 36 subjects with MDS will be enrolled in the phase 1a dose escalation cohorts; each dose escalation cohort will enroll a minimum of 3 and a maximum of 9 evaluable subjects.

### 3.1.4 Dose Escalation Rules for Groups 2 and 3

For both Group 2 and Group 3, a minimum of 3-4 subjects will be enrolled initially into each cohort and additional subjects up to a maximum of 9 evaluable subjects will be added at the Sponsor's discretion. After all subjects in each dose escalation cohort have either completed the DLT evaluation period or had a DLT, the DLRT will meet to determine whether it is appropriate to escalate or de-escalate the dose, or whether to stop the study for safety concerns. The DLRT will evaluate all available safety, laboratory, PK, and PD data to guide their dose-finding recommendations. **Based on DLRT recommendation, selected target dose levels, with the exception of the maximal tested dose, may be skipped in Groups 2 and 3 dose escalation cohorts if these dose levels have been evaluated in subjects with R/R AML (Group 1) and deemed safe.** [Appendix H](#) shows the mTPI-2 escalation/de-escalation guideline with a

target toxicity probability of 0.25 and an acceptable toxicity probability interval of 0.20 to 0.30. A dose level will be considered unsafe, with no additional subjects enrolled at that dose level, if it has an estimated  $> 95\%$  probability of exceeding the target DLT rate  $p_T$  (ie,  $P [DLT > p_T | \text{data}] > 95\%$ ) with at least 3 subjects treated and evaluated at that dose level. Dose exploration will continue until the current recommended dose cohort reaches at least 6 evaluable subjects or until the highest protocol-defined dose has been evaluated.

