#### **6.2.1.4 Dose-cohort Study Escalation and Stopping Rules, Dose-limiting Toxicities (DLTs)**

For R/R AML (Group 1), dose escalation decisions will be made in accordance with a standard 3+3 design using the rules noted below.

- If no DLT is observed within the DLT window in the initial 3 subjects of a cohort, then dose escalation to the next higher dose level cohort will occur.
- If 1 DLT is observed within the DLT window in the initial 3 subjects of a cohort, then the cohort will be expanded to 6 subjects. If no further DLT(s) are observed in the 6 subjects, then dose escalation to the next higher dose level cohort will occur. If  $\geq 2$  subjects experience a DLT in a cohort, then enrollment into this cohort will be stopped.
- see Section 3.4 for replacement of subjects.

Dose escalation will occur at the planned dose levels until the MTD is determined or until the highest dose level is tested. The MTD is defined as the highest dose level with an observed incidence of DLT in < 33% of subjects enrolled in a cohort dose level. At least 6 evaluable subjects will be treated at the MTD or highest tested dose.

For MRD+ AML (Group 2) and MDS (Group 3), dose exploration will be guided by prespecified monitoring rules (Appendix H), which is based on a modified toxicity probability interval algorithm (mTPI-2; Guo et al, 2017) with a target DLT rate of 25% and an acceptable toxicity probability interval of 20%-30%. Consistent with conventional oncology phase 1 study designs (eg, 3 + 3 design) and given the imprecision with making decisions using as few as 3 subjects, in the instance of 1 DLT in the initial 3 subjects at a dose level then, as appropriate, the design allows expansion at the dose level beyond 3 subjects.

The mTPI-2 algorithm employs a simple beta-binomial Bayesian model. Let  $p_t$  be the target toxicity level and  $(p_t - \epsilon_1, p_t + \epsilon_2)$  be the equivalence toxicity interval denoted as EI. The unit toxicity interval  $(0, 1)$  is divided into subintervals with equal length given by  $(\epsilon_1 + \epsilon_2)$ . Let the under-dosing intervals (LI) denote for a set of intervals below EI, and the overdosing intervals (HI) for a set of intervals above EI. The 3 types of dosing intervals (EI, LI, HI) are associated with 3 different dose escalation decisions. The LI correspond to a dose escalation (E), the HI correspond to a dose de-escalation (D), and proper

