dosing intervals (EI) correspond to staying at the current dose (S). This study design uses a target toxicity level,  $p_T$  of 25%, and EI of (20%, 30%).

Decision rules are based on the unit probability mass (UPM) calculated on these equal-length intervals. Given an interval and a probability distribution, the UPM of that interval is defined as the probability of the interval divided by the length of the interval. If the interval with the largest UPM is from LI, EI or HI, then the corresponding dose decision would be E, S, or D, respectively.

A dose level will be considered unsafe, with no additional subjects enrolled at that dose level, if it has an estimated 95% or more probability of exceeding the target DLT rate  $p_T$  (ie,  $P [DLT > p_T | \text{data}] > 95\%$ ) with at least 3 evaluable subjects treated and evaluated at that dose level.

After the escalation phase is completed, final DLT rates at each dose level will be estimated by isotonic regression (Ji et al, 2010). The MTD will be determined as the dose level with the DLT estimate closest to the target toxicity level of 25%. In the case of dose levels with estimated toxicity of equal distance (tied dose levels) from the target toxicity of 25%, the following approach will be used (Ji et al, 2010): among all tied dose levels the highest dose level with target toxicity  $\leq 25\%$  will be selected, unless all tied dose levels have estimated toxicity  $> 25\%$ , in which case the lowest dose level will be selected.

A DLT will be defined as any of the events described below occurring in a subject during the DLT window, unless clearly attributable to causes other than AMG 330. The DLT window will be 4 weeks, regardless of the length of the treatment cycle. The CTCAE will be used to assess toxicities/adverse events with the exception of cytokine release syndrome (see [Table 7](#) for grading of cytokine release syndrome).

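### The escalation rules do not say how a subject with ongoing grade 4 neutropenia counts when the 4-week DLT window closes, although the neutropenia DLT cannot be met before day 42

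*Protocol*

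**What the plan says.** Protocol Section 6.2.1.4 fixes the window: "The DLT window will be 4 weeks, regardless of the length of the treatment cycle". An event is a DLT only if it occurs in that window.

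The DLT list in the same section has one item based on a cytopenia. It is grade 4 neutropenia persisting to at least "42 days from start of cycle in absence of evidence of active AML (in case of 3 or 4 weeks treatment cycles", it adds, "the number of days would increase accordingly"). No day counts are given for the longer cycles.

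The decisions hang on the window. For Group 1, Sections 3.1.1 and 6.2.1.4 state: "If no DLT is observed within the DLT window in the initial 3 subjects of a cohort, then dose escalation to the next higher" level follows, and Table 5 turns the counts into actions. For Groups 2 and 3, Section 3.1.4 states: "After all subjects in each dose escalation cohort have either completed the DLT evaluation period or had a DLT, the DLRT will meet", and the mTPI-2 table in SAP Section 3.3 guides the action.

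There is one provision for late events. Section 6.2.1.4 permits, but does not require, a longer window in any cohort: "retrospectively to assess events starting or persisting outside the window in case the DLT definition is time dependent". Neutropenia is its example. The only hold on escalation that is tied to DLT assessment is that at least 3 subjects must be DLT-evaluable.

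**The concern.** The criterion day lies after the window closes. A subject who has completed the window with enough days at target dose is evaluable and enters the denominator. If that subject still has grade 4 neutropenia, no DLT has been observed within the window, so the rules as written count a non-DLT. The extension clause lets the event be attributed to its dose later. It does not say what the subject counts as on the day of the decision, or whether the decision is looked at again.

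At stake is an escalation taken on an incomplete count. Myelosuppression, neutropenia in particular, is expected (Protocol Section 2.3). Groups 2 and 3 enroll 3 to 4 subjects initially into each cohort (Section 3.1.4), and the 6-day interval after the first subject is written only in the Group 1 section. Several subjects could therefore be started at the next dose before the earlier cohort's neutropenia is resolved.

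**Working it through.** **The plan's own figures.** Protocol Section 10.2 gives the chance of seeing at least one DLT for true rates of 10% to 33%, which is 1 − (1 − p)^n:

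- n = 3: 1 − 0.90³ = 27.1% and 1 − 0.67³ = 69.9% (stated 27-70%).
- n = 6: 1 − 0.90⁶ = 46.9% and 1 − 0.67⁶ = 91.0% (stated 47-91%).

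They reproduce. They treat every DLT as visible at the decision, which is not so for this criterion.

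**Timing gap for a subject at day 28.** Inputs: window of 28 days; criterion day 42 for a 2-week cycle. Days 49 and 56 assume that the count rises by 7 and 14 days with the cycle.

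| Cycle | Criterion day | Short at day 28 | Short at day 34 |
|---|---|---|---|
| 2 weeks | 42 | 14 | 8 |
| 3 weeks | 49 (assumed) | 21 | 15 |
| 4 weeks | 56 (assumed) | 28 | 22 |

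The last column is the first subject of a quickly filled Group 1 cohort. With the minimum 6-day interval, a last subject who starts on day 7 reaches its own day 28 when the first subject is at day 34. Groups 2 and 3 appear only in the 28-day schedules (Tables 12 and 13), so the 4-week row is theirs.

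**What one case does to the action** (Table 5; SAP Section 3.3 table):

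- 0/3 is escalate in both. 1/3 is enroll three more (Table 5) or stay (mTPI-2).
- 1/6 is escalate in both. 2/6 is de-escalate in both.

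**Illustration for the 3+3.** P(escalate) = (1 − p)³ + 3p(1 − p)⁵. The documents give no rate of late neutropenia DLTs, so a range is assumed. The early DLT rate is set at 10%, and late events are taken as independent of early ones, so the total is p = 1 − 0.90 × (1 − late rate).

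On day-28 data p = 0.10, and P(escalate) = 0.729 + 0.177 = 91%. With all DLTs known:

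| Assumed late rate | Total p | P(escalate) | At least one late case in 3 | In 6 |
|---|---|---|---|---|
| 5% | 0.145 | 82% | 14% | 26% |
| 10% | 0.190 | 73% | 27% | 47% |
| 20% | 0.280 | 54% | 49% | 74% |
| 30% | 0.370 | 36% | 66% | 88% |

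The late rate here means subjects who go on to meet the full criterion, not everyone neutropenic at day 28. The 91% applies only if every subject is judged at day 28, the window is not extended and the DLRT does not act on what it sees.

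**The case against.** The plan is far from blind to ongoing neutropenia. Protocol Section 10.3.1 has adverse events and DLTs assessed continually and fed into all enrollment and dosing decisions, and allows a cohort's enrollment to be suspended at any time. Under Section 10.3.2 the DLRT reviews toxicities of grade 3 or higher that fall short of a DLT, and can recommend a delay in dosing or a different DLT period. Section 6.2.1.4 lets it declare an event outside the window a DLT by unanimous decision. In Groups 2 and 3 escalation is a DLRT judgment on all available data. A reader might infer that nothing can hold escalation or reopen it; these provisions show otherwise. What they leave is discretion: none fixes the count that enters either table.

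A reader might also infer that no subject can have met the criterion at any decision. That is too strong. The decision waits for the last evaluable subject. In Group 1, where no more than 3 subjects should enter a cohort in two weeks, six subjects take about 14 days or more, so the first is at about 14 + 28 = day 42. Section 3.5 plans about 5 years for about 70 Group 1 subjects, or 70/60, just over one a month. Early subjects in a slow cohort may well be past the criterion day. The last ones are not, at any pace.

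Nor do the documents support calling this the DLT most attributable to the drug. They list cytokine release syndrome as an identified risk and cytopenia as a potential one (Tables 1 and 2). Some serious consequences of neutropenia are caught inside the window, since infection and bleeding are exempt only when due to active leukemia.

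Finally, the amendment history gives reasons for the present window: an earlier post-cycle interval had not helped to capture shifts in myeloid counts, and the 4-week minimum followed regulatory feedback. That explains the window's length. It does not settle how a pending subject is counted.

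**Conclusion.** The point stands as a conflict between the DLT definition and the decision time, together with a missing counting rule. Decisions are tied to a 4-week window; the neutropenia criterion cannot be met before day 42, and later for longer cycles. For the most recently enrolled subjects the shortfall is 14 days with 2-week cycles, and 21 or 28 days under the assumed shift for 3- and 4-week cycles. The default count for a subject still neutropenic is a non-DLT. That is a reading of the rules, since no sentence states it, and one case is enough to change the action at 0/3 or 1/6.

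The size of the effect in this trial is unknown. The probabilities above rest on assumed late rates of 5% to 30%, a 10% early rate, independence and no DLRT intervention.

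A reader might infer that late cases are lost for good, or that the final MTD is biased. The documents do not support that: the retrospective extension allows later attribution, and the final MTD estimate uses all DLT-evaluable subjects from escalation and expansion. The exposed step is the escalation decision itself. The criterion also counts from the start of the cycle, so it should not be read as 42 days of grade 4 neutropenia.

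**What to change.** Reconcile Protocol Sections 3.1.1, 3.1.4 and 6.2.1.4 with SAP Sections 3.3 and 7.1 so that the neutropenia DLT and the decision time agree, and give the day counts for 3- and 4-week cycles. Then state that:

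- a subject with ongoing grade 4 neutropenia and no active disease at the end of the window is flagged as pending, not entered as a non-DLT;
- the DLRT is shown the Table 5 or mTPI-2 decision with each pending subject counted both ways;
- the cohort's table decision is re-evaluated when a pending or late event resolves or is classified as a DLT.

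The text should also say to which cycle and dose a late event is attributed. By day 42 to 56 a subject may be in cycle 2, possibly at a higher dose, and Section 3.1.1 does not count DLTs at that higher dose in 3+3 decisions. SAP Section 5.4 takes DLT status from a yes on the Events eCRF, so pending status needs its own listing for the review meeting.

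The window length, the criterion and the clinical handling remain the sponsor's choice. The cost is wording and one listing, because hematology is already taken at the weekly visits in the infusion-free interval. If the sponsor chooses to wait, the delay is about 2 to 4 weeks, and only in cohorts where a pending subject would change the decision.

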#### **6.2.1.5 Dosage Adjustments, Delays, Rules for Withholding or Restarting, Permanent Discontinuation**

##### **Criteria for Dose Delay or Dose Reduction**

Any clinically relevant (as determined by the investigator) grade 4 adverse event related to IP that does not meet the DLT criteria should lead to a dose delay and/or a dose reduction. The decision if a dose delay or reduction will be performed is up to the investigator's discretion. The sponsor may be consulted.

In case of grade 2 cytokine release syndrome, treatment can be continued on the currently tested dose level for 8 hours. If symptoms do not improve to grade 1, the dose will be de-escalated by 50% for an additional 24 hours. If CRS grade 2 resolves to grade 1, the dose can be re-escalated back to the level being tested. If symptoms persist, AMG 330 will be interrupted until symptoms improve to grade 1. If treatment is interrupted for < 24 hours, the interrupted dose can be resumed and re-escalated back to the tested dose level. If treatment is interrupted for > 24 hours, restart or repeat rules apply (see below).

In case of grade 3 cytokine release syndrome, treatment must be interrupted. The Amgen medical monitor has to be consulted prior to a planned restart.

In case of grade 4 cytokine release syndrome, treatment must be permanently discontinued. See Section [6.6](#) for specific instructions for the management of cytokine release syndrome.

Dose delay: treatment should be interrupted until the event is resolved to grade  $\leq 1$ , and can then be resumed at the same dose unless the interruption lasted for more than 24 hours, please see below. (Note: if the event needs > 21 days to resolve, treatment has to be permanently discontinued, see also below).

Dose reduction: treatment may be resumed after the event is resolved to grade  $\leq 1$  or immediately at the investigator's discretion at the previous (lower) dose level.

Re-escalation to the target dose can be considered if the event has resolved to  $\leq$  grade 1 if applicable.

In case of re-appearance of the same grade 4 adverse event, IP should be permanently discontinued.

For persistent or re-occurring clinically relevant grade 3 adverse event related to IP, a dose delay or a dose reduction should be considered.

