### **Infusion Interruption**

Significant events requiring a change in treatment will be managed by immediate infusion interruption:

- The subject experiences a DLT as defined in Section [6.2.1.4](#)
- The subject experiences a clinically relevant grade 4 adverse event related to IP (see above)
- The subject experiences a grade  $\geq 2$  cytokine release syndrome that does not respond to medical management as described in [Table 7](#)
- The subject meets criteria for discontinuation of IP as described in Section [8.3](#)
- Technical problem with the infusion pump
- The investigational product is incorrectly prepared or administered (eg, overdose)

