**Table 7. Grading and Management of Cytokine Release Syndrome**

CRS Grade	Description of Severity a	Minimum Expected Intervention c	Instructions for Interruption of AMG 330
1	Symptoms are not life threatening and require symptomatic treatment only, eg, fever, nausea, fatigue, headache, myalgias, malaise	

Administer symptomatic treatment (eg, paracetamol/ acetaminophen for fever, fluids for hypotension).

Monitor for CRS symptoms including vital signs and pulse oximetry at least Q2 hours for 12 hours or until resolution, whichever is earlier.

	N/A
2	Symptoms require and respond to moderate intervention  Oxygen requirement < 40%, OR  Hypotension responsive to fluids or low dose of one vasopressor, OR  Grade 2 organ toxicity or grade 3 transaminitis per CTCAE criteria	
Administer:
 

Symptomatic treatment (eg, paracetamol/ acetaminophen for fever; vasopressors for hypotension)

Supplemental oxygen when oxygen saturation is < 90% on room air

Intravenous fluids or low dose vasopressor for hypotension when systolic blood pressure is < 100 mmHg. Persistent tachycardia (eg >120 bpm) may also indicate the need for intervention for hypotension.

Consider use of tocilizumab 8 mg/kg iv. Up to 3 additional doses can be given 8 hours apart, if needed.

 
Monitor for CRS symptoms including vital signs and pulse oximetry at least Q2 hours for 12 hours or until resolution to CRS grade ≤ 1, whichever is earlier.
 
For subjects with extensive co-morbidities or poor performance status, manage per grade 3 CRS guidance below.
	
Institute medical management. If hypotension persists 8 hours after adequate medical management, de-escalate AMG 330 to 50% of the current dose for 24 hours. If symptoms persist, interrupt AMG 330. Refer Section 6.2.1.5 for dose interruption guidelines. If symptoms improve to <= Grade 1, re-escalate to the dose at which the CRS event previously occurred. If symptoms progress to grade 3 criteria, see row below.
 
Permanently discontinue AMG 330 if there is no improvement to CRS ≤ grade 1 within 7 days.

Footnotes defined on next page of table

Page 1 of 2

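### For grade 2 CRS that persists without hypotension, Section 6.2.1.5 requires a 50% dose reduction that Table 7 states only for hypotension, and neither text has precedence

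*Protocol*

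**What the plan says.** Three places in the current protocol text deal with grade 2 CRS that does not settle.

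- **Section 6.2.1.5, Criteria for Dose Delay or Dose Reduction.** "In case of grade 2 cytokine release syndrome, treatment can be continued on the currently tested dose level for 8 hours". Then: "If symptoms do not improve to grade 1, the dose will be de-escalated by 50% for an additional 24 hours". The trigger is symptoms in general. If they still persist, the infusion is interrupted until grade 1.
- **Section 6.6, Table 7, grade 2 row.** "If hypotension persists 8 hours after adequate medical management, de-escalate AMG 330 to 50% of the current dose for 24 hours". The cell continues "If symptoms persist, interrupt AMG 330" and "Refer Section 6.2.1.5 for dose interruption guidelines".
- **Section 6.2.1.5, Infusion Interruption.** Among the events to be handled by interrupting at once, the list includes CRS of grade 2 or higher, described as "cytokine release syndrome that does not respond to medical management as described in" Table 7. It mentions neither an 8-hour period nor a 50% step.

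Hypotension is not needed for grade 2. The severity column of the same Table 7 row also lists "Oxygen requirement < 40%, OR" and "Grade 2 organ toxicity or grade 3 transaminitis per CTCAE criteria", and each criterion is sufficient alone.

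**The concern.** A subject can have grade 2 CRS, without low blood pressure, that outlasts the 8 hours. The general rule in Section 6.2.1.5 requires the dose to be halved. The table to which sites are sent for CRS management states that step for hypotension only. Section 3.1.6.1 sends Group 4 investigators to Table 7 specifically, so both texts will be in use.

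The case is foreseeable. Section 2.1.3 calls CRS a frequent toxicity of AMG 330 in R/R AML. Table 2 lists hypoxemia and transaminitis among its signs, and aminotransferase elevation as an identified risk in its own right. CRS is also part of the DLT definition, so contradictory dosing instructions for it are undesirable in a dose-finding study even where the exposure difference is small.

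**Working it through.** The documents state no figure on this point, so there is none to reproduce. The check sets the two dosing instructions side by side and then sizes one 24-hour step.

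| | Section 6.2.1.5 | Table 7, grade 2 row |
|---|---|---|
| Trigger for the 50% step | Any symptoms not improved to grade 1 | Persisting hypotension |
| Start of the 8 hours | Continued treatment on the tested dose | After adequate medical management |
| Size and length | 50% for 24 hours | 50% for 24 hours |
| Next step | Interrupt if symptoms persist | Interrupt if symptoms persist |
| Cross-reference | To Section 6.6 for CRS management | To Section 6.2.1.5 for interruption |

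**Case 1: persisting hypotension.** Both texts lead to 50% for 24 hours. They agree on the step, although the 8 hours may start at different times.

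**Case 2: persisting grade 2 CRS without hypotension** (oxygen requirement below 40%, grade 2 organ toxicity or grade 3 transaminitis). Section 6.2.1.5 requires 50% for 24 hours. Table 7 names no reduction. Its sentence on interrupting for persisting symptoms follows the hypotension sentence, and it is not clear whether it applies to a subject whose dose was never reduced.

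**Precedence.** Each text refers to the other. Section 6.2.1.5 points to Section 6.6 for CRS management, and Table 7 points back for interruption, not for the 50% reduction. Neither is said to govern.

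**Infusion Interruption list.** It can be read as the last step, after the halving has failed, or as a rule that replaces the halving once medical management has failed. The wording does not settle which.

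**Size of one step.** SAP Section 5.1 defines cumulative dose as duration in days times dose per day, summed. With the assigned daily dose as the unit:

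- no reduction for 24 hours: 1 × 1.0 = 1.0 dose-day;
- halved for 24 hours: 1 × 0.5 = 0.5 dose-day;
- difference: 1.0 − 0.5 = 0.5 dose-day.

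As a share of time at target dose, 0.5/7 = 7.1%, 0.5/14 = 3.6% and 0.5/28 = 1.8%. The 7 and 14 days are the minimum target-dose periods for DLT-evaluability in Section 6.2.1.4; 28 days is the longest infusion.

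**The case against.** The best defence is that this is loose wording in one table cell, not two policies. Table 7 is silent on non-hypotensive cases: it neither orders the full dose nor forbids a reduction. Its next sentences return to symptoms in general, and it sends the reader to Section 6.2.1.5, where the general grade 2 rule stands. The summary of changes at the end of the protocol describes the dose reduction as covering grade 2 CRS unresolved at 8 hours, without limiting it to hypotension. A site that reads both passages will find an instruction.

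Part of this stands. The texts can be harmonised, and a careful reader may do so. But the cross-reference names interruption, not reduction; a summary of changes does not govern current text; and the difference in when the 8 hours start remains on any reading.

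A reader might also infer that the three passages give three distinct actions, so that the subject receives 100%, 50% or 0% of the assigned dose over the next 24 hours. The documents do not support that as stated. The 100% comes from Table 7's silence. The 0% requires the Infusion Interruption list to apply at 8 hours, and that list has no clock and can be read as the end of the same sequence. What stands is that its place in the sequence is not stated.

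**Conclusion.** The inconsistency is real and narrow. It concerns grade 2 CRS that persists without hypotension, where the trigger for the 50% step differs between Section 6.2.1.5 and Table 7. The start of the 8 hours also differs, no precedence is given, and the place of the Infusion Interruption list is unclear. Sites following different passages can dose the same subject differently; the documents do not show that they will or did. The direct exposure gap between halving and no reduction is 0.5 dose-days per event.

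A reader might infer that DLT counts or DLT-evaluability are compromised. The documents do not show this:

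- Grade 2 CRS becomes a DLT if it has not resolved to grade 1 within 7 days, with or without intervention (Section 6.2.1.4). That limit is the same whichever passage is followed, and nothing indicates that a 24-hour halving moves subjects across it.
- Section 6.2.1.5 lets target-dose days before and after an interruption be added together.
- Section 6.6 places the raised CRS risk in the first few days after the initial infusion. Where dose steps are used, those are generally run-in or step days rather than target-dose days.
- A larger effect would need an interruption of more than 24 hours, which brings in the restart rules. Both texts already lead to interruption if symptoms persist.

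The conclusion rests on the wording alone. The frequency of persisting non-hypotensive grade 2 CRS is not given, so no trial-level size can be stated.

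**What to change.** The sponsor should reconcile the grade 2 CRS paragraph of Section 6.2.1.5, the Infusion Interruption list in the same section and the grade 2 row of Table 7, so that all three state:

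- one trigger for the 50% step, covering explicitly every criterion by which Table 7 assigns grade 2;
- one starting point for the 8 hours;
- one sequence, saying whether interruption follows the 50% step or replaces it.

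One of the texts should be named as governing, with the others referring to it. Which clinical rule is right is for the sponsor and its clinical advisers; this review takes no position. The change is to protocol wording only. It needs no new data collection, sample size or analysis.
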